## 15.3. Schedule of Study Procedures

[figure not shown]
Table 6 Schedule of Assessments Screening to Day 113(Week 16)

Visit	1		2 b	3	4	5	6 a	7 a	8 a	9 a	ET #
Visit days	-29 to -8	-7 to 1	1	8	15	22	29	57	85	113	-
Visit weeks	-4 to -1	- 1	0	1	2	3	4	8	12	16	-
Visit window (days)	0	0	0	±3	±3	±3	±3	±3	±3	±3	-
	Screening		Baseline	Treatment							
Description	Clinic		Clinic	Clinic	Clinic	Telephone m Error! Reference source not found.	Clinic	Clinic	Clinic	Clinic	Clinic
Informed consent	X										
Demographics	X										
Medical history	X										
Concomitant medications - including emollients	X		X a	X	X	X	X	X	X	X	X
AEs (including SAEs)	<----->										X
Inclusion/exclusion criteria	X		X								
Physical examination	X		X		X		X	X	X	X	X
Body weight and height (height at Screening only)	X		X							X	X
Vital signs c	X		X				X	X	X	X	X
12-lead ECG	X		X					X		X	X
EASI	X		X		X		X	X	X	X	X
BSA	X		X		X		X	X	X	X	X
IGA	X		X		X		X	X	X	X	X

Visit	1		2 b	3	4	5	6 a	7 a	8 a	9 a	ET #
Visit days	-29 to -8	-7 to 1	1	8	15	22	29	57	85	113	-
Visit weeks	-4 to -1	- 1	0	1	2	3	4	8	12	16	-
Visit window (days)	0	0	0	±3	±3	±3	±3	±3	±3	±3	-
	Screening		Baseline	Treatment							
Description	Clinic		Clinic	Clinic	Clinic	Telephone m Error! Reference source not found.	Clinic	Clinic	Clinic	Clinic	Clinic
SCORAD Index i	X		X				X	X	X	X	X
DLQI i			X		X			X		X	X
ADCT i			X							X	X
HADS i			X					X		X	X
Blood samples for virology (HIV, Hepatitis B and C) and TB (QuantiFERON ® -TB Gold blood test) Error! Reference source not found.	X										
Safety tests (FBC, non-fasting biochemistry, electrolytes, urinalysis), FSH for post-menopausal women at Screening	X k		X				X	X	X	X	X
Pregnancy test – females only (serum at Screening, urine thereafter) c	X		X				X	X	X	X	X
Blood samples for serum concentrations of KY1005 (PK) a			X a	X	X		X	X	X	X	X
Blood samples for serum concentrations of ADAs d											

Visit	1		2 b	3	4	5	6 a	7 a	8 a	9 a	ET #
Visit days	-29 to -8	-7 to 1	1	8	15	22	29	57	85	113	-
Visit weeks	-4 to -1	- 1	0	1	2	3	4	8	12	16	-
Visit window (days)	0	0	0	±3	±3	±3	±3	±3	±3	±3	-
	Screening		Baseline	Treatment							
Description	Clinic		Clinic	Clinic	Clinic	Telephone m Error! Reference source not found.	Clinic	Clinic	Clinic	Clinic	Clinic
POEM i			X				X	X	X	X	X
NRS (pruritus) – internet-enabled device g		X h Error! Reference source not found.	X	→	→	→	→	→	→	→	→
Contact IRT	X		X	X	X	X	X	X	X	X	X
Randomisation i Error! Reference source not found.			X								
IMP administration and check of local skin reaction j,o			X				X	X	X	X	

Index; ECG=electrocardiogram; FBC=full blood count; FSH=follicle-stimulating hormone; HADS= Hospital Anxiety and Depression Scale; HIV=human immunodeficiency virus; IgE=immunoglobulin E; IMP=Investigational Medicinal Product; NRS=Numerical Rating Scale; POEM=Patient Oriented Eczema Measure; PK=pharmacokinetics; PRO=patient reported outcome; SAE=serious adverse event; SCORAD=SCORing of Atopic Dermatitis; TB=tuberculosis; IGA= Investigator Global Assessment.

# Early Termination could be done by the Investigator (see Section 3.4, Section 3.5 and Section 9 of protocol).

a On IMP administration days, all assessments, including taking blood samples, will be performed pre-injection unless stated otherwise.

b Baseline assessments may be performed up to 24 hours prior to the first IMP injection (Day 1).

c On IMP administration days up to and including Day 113 (Week 16) vital signs will be measured pre-injection and at 15-, 30- and 60-minutes post-injection. The tolerance on vital signs measurements after dosing is  $\pm 5$  minutes.

d [Redacted]

e If urine pregnancy test is positive, a serum control must be done before IMP administration

f [Redacted]

g NRS (pruritus) will be recorded daily, ideally in the morning, based on the previous 24 hours, with worst (maximum) itch intensity recorded.

h Patients will be asked to assess their worst itching due to atopic dermatitis over the last 7 days prior to Baseline on an NRS anchored by the terms “no itch” (0) and “worst itch imaginable” (10).

i May be performed up to 24 hours prior to first injection as long as all inclusion/exclusion criteria are satisfied.

- j* [REDACTED]
- k* Screening laboratory assessments may be repeated a maximum of once where initial results are in the Investigator's opinion, clinically significant
- l* Where possible, the PRO assessments completed at the study site are to be completed by patients prior to the completion of other study assessments and the administration of IMP.
- m* A telephone visit is defined as a videoconference, video call or telephone call.
- n* [REDACTED]
- o* [REDACTED]

**Table 7 Schedule of Assessments - Day 120 (Week 17) to Day 169(Week 24)**

Visit	10	11 a	12	13	14	15 a	ET #
Visit days	120	141	148	155	162	169	-
Visit weeks	17	20	21	22	23	24 k	-
Visit window (days)	±1	±3	±1	±1	±1	±3	-
	Treatment						-
Description	Clinic	Clinic	Telephone h	Telephone h	Telephone h	Clinic	Clinic
Concomitant medications – including emollients	X	X	X	X	X	X	X
AEs (including SAEs)	←----->						X
Physical examination							X
Vital signs b		X				X	X
12-lead ECG						X	X
EASI		X				X	X
BSA		X				X	X
IGA		X				X	X
SCORAD Index g		X				X	X
DLQI g		X				X	X
ADCT g						X	X
HADS g		X				X	X
Safety tests (FBC, non-fasting biochemistry, electrolytes, urinalysis)		X				X	X
Pregnancy test - females only (urine) i		X				X	X
Blood samples for serum concentrations of KY1005 (PK) a	X	X				X	X

Visit	10	11 a	12	13	14	15 a	ET #
Visit days	120	141	148	155	162	169	-
Visit weeks	17	20	21	22	23	24 k	-
Visit window (days)	±1	±3	±1	±1	±1	±3	-
	Treatment						-
Description	Clinic	Clinic	Telephone h	Telephone h	Telephone h	Clinic	Clinic
Blood samples for serum concentrations of ADAs c							
POEM g		X				X	X
NRS (pruritus) – internet-enabled device d	→	→	→	→	→	→	→
Contact IRT	X	X	X	X	X	X	X
Re-randomisation						X e	
IMP administration and check of local skin reactionf, g, j		X				X	

ADA=anti-drug antibody; ADCT=atopic dermatitis control tool; AEs=adverse events; BSA=body surface area; DLQI=Dermatology Quality of Life Index; EASI=Eczema Area and Severity Index; ECG=electrocardiogram; FBC=full blood count; IgE=immunoglobulin E; IMP=Investigational Medicinal Product; NRS=Numerical Rating Scale; POEM=Patient Oriented Eczema Measure; PK=pharmacokinetics; PRO=patient reported outcome; SAE=serious adverse event; SCORAD=SCORing of Atopic Dermatitis; IGA= Investigator Global Assessment; HADS= Hospital Anxiety and Depression Scale.

# Early Termination Visit could be done by the Investigator (see Section 3.4, Section 3.5 and Section 9 of protocol).

a On IMP administration days, all assessments, including taking blood samples, will be performed pre-injection unless stated otherwise.

b On IMP administration days vital signs will be measured pre-injection and 30 minutes post injection. The tolerance on vital signs after dosing is ±5 minutes.

c [REDACTED]

d NRS (pruritus) will be recorded daily, ideally in the morning, based on the previous 24 hours with worst (maximum) itch intensity recorded.

e Where IMP administration occurs on a re-randomisation day the IMP injection is to be administered after re-randomisation (with the new regimen where applicable).

f [REDACTED]

g Where possible, the PRO assessments completed at the study site are to be completed by patients prior to the completion of other study assessments and the administration of IMP.

h A telephone visit is defined as a videoconference, video call or telephone call.

i If urine pregnancy test is positive, a serum control must be done before IMP administration

j [REDACTED]

- k The ICF from the DRI/Phase2b/parent study will not be valid as LTE informed consent. In order for patients to roll over to the LTE study, a specific LTE ICF will need to be applied, agreed upon and signed at the LTE study, as the LTE is a separated protocol.

**Table 8 Schedule of Assessments - Day 176 (Week 25) to Day 365(Week 52)**

Visit	16	17 a	18	19 a	20	21 a	22 a	23	24 a	25	26 a	27	28 a	ET #
Visit days	176	197	204	225	232	253	281	288	309	316	337	344	365	
Visit weeks	25 i	28 i	29 i	32 i	33 i	36 i	40 i	41 i	44 i	45 i	48 i	49 i	52 i	
Visit window (days)	±1	±3	±1	±3	±1	±3	±3	±1	±3	±3	±3	±1	±3	
	Treatment													-
Description	Clinic	Clinic	Telephon e f	Clinic	Telephon e f	Clinic	Clinic	Telephon e f	Clinic	Telephon e f	Clinic	Telephon e f	Clinic	Clinic
Concomitant medications - including emollients	X	X	X	X	X	X	X	X	X	X	X	X	X	X
AEs (including SAEs)	←----->													X
Physical examination		X					X						X	X
Vital signs b		X		X		X	X		X		X		X	X
12-lead ECG				X			X				X		X	X
EASI		X		X		X	X		X		X		X	X
BSA		X		X		X	X		X		X		X	X
IGA		X		X		X	X		X		X		X	X
SCORAD Index g		X		X		X	X		X		X		X	X
DLQI g		X		X		X	X		X		X		X	X
ADCT g						X							X	X

Visit	16	17 a	18	19 a	20	21 a	22 a	23	24 a	25	26 a	27	28 a	ET #
Visit days	176	197	204	225	232	253	281	288	309	316	337	344	365	
Visit weeks	25 i	28 i	29 i	32 i	33 i	36 i	40 i	41 i	44 i	45 i	48 i	49 i	52 i	
Visit window (days)	±1	±3	±1	±3	±1	±3	±3	±1	±3	±3	±3	±1	±3	
Treatment														-
Description	Clinic	Clinic	Telephone e	Clinic	Telephone e	Clinic	Clinic	Telephone f	Clinic	Telephone e	Clinic	Telephone e	Clinic	Clinic
HADS g		X		X		X	X		X		X		X	X
Safety tests (FBC, non-fasting biochemistry, electrolytes, urinalysis)		X		X		X	X		X		X		X	X
Pregnancy test - females only (urine) i		X		X		X	X		X		X		X	X
Blood samples for serum concentrations of KY1005 (PK) a	X	X		X		X	X		X		X		X	X
Blood samples for serum concentrations of ADAs c														

Visit	16	17 a	18	19 a	20	21 a	22 a	23	24 a	25	26 a	27	28 a	ET #
Visit days	176	197	204	225	232	253	281	288	309	316	337	344	365	
Visit weeks	25 i	28 i	29 i	32 i	33 i	36 i	40 i	41 i	44 i	45 i	48 i	49 i	52 i	
Visit window (days)	±1	±3	±1	±3	±1	±3	±3	±1	±3	±3	±3	±1	±3	
Treatment														-
Description	Clinic	Clinic	Telephone e	Clinic	Telephone e	Clinic	Clinic	Telephone f	Clinic	Telephone e	Clinic	Telephone e	Clinic	Clinic
POEM g				X		X	X		X		X		X	X
NRS (pruritus) - internet-enabled device d	→	→	→	→	→	→	→	→	→	→	→	→	→	→
Contact IRT	X	X	X	X	X	X	X	X	X	X	X	X	X	X
IMP administration and check of local skin reaction e		X		X		X	X		X		X			

ADAs=anti-drug antibodies; ADCT=atopic dermatitis control tool; AEs=adverse events; BSA=body surface area; DLQI=Dermatology Quality of Life Index; EASI=Eczema Area and Severity Index; ECG=electrocardiogram; FBC=full blood count; IgE=immunoglobulin E; IMP=Investigational Medicinal Product; NRS=Numerical Rating Scale; POEM=Patient Oriented Eczema Measure; PK=pharmacokinetics; PRO=patient reported outcome; SAE=serious adverse event; SCORAD=SCORing of Atopic Dermatitis; IGA= Investigator Global Assessment; HADS= Hospital Anxiety and Depression Scale.

# Early Termination could be done by the Sponsor or the Investigator (see Section 3.4, Section 3.5 and Section 9 of protocol).

a On IMP administration days in this time period, all assessments, including taking blood samples, will be performed pre-injection unless stated otherwise.

b On IMP administration days in this time period, vital signs will be measured pre-injection and 30 minutes post- injection. The tolerance on vital signs after dosing is ±5minutes.

- c [REDACTED]
- d NRS (pruritus) will be recorded daily, ideally in the morning, based on the previous 24 hours with worst (maximum) itch intensity recorded.
- e [REDACTED]
- f A telephone visit is defined as a videoconference, video call or telephone call.
- g Where possible, the PRO assessments completed at the study site are to be completed by patients prior to the completion of other study assessments and the administration of IMP.
- i If urine pregnancy test is positive, a serum control must be done before IMP administration.
- j The ICF from the DRI/Phase2b/parent study will not be valid as LTE informed consent. In order for patients to roll over to the LTE a specific LTE ICF will need to be applied, agreed upon and signed at the LTE study, as the LTE is a separated protocol.

**Table 9 Schedule of Assessments – Safety Follow-up**

Visit	29 a	30 a	31 a	32 a	ET #
Visit days	393	421	449	477	
Visit weeks	56 d	60 d	64 d	68 d	
Visit window (days)	±7	±7	±7	±7	
Description	Clinic	Telephone b	Clinic	Clinic	Clinic
Concomitant medications - including emollients	X	X	X	X	X
AEs (including SAEs)	☐-----☐				X
Physical examination			X	X	X
Vital signs	X		X	X	X
12-lead ECG	X		X	X	X
Safety tests (FBC, non-fasting biochemistry, electrolytes, urinalysis)	X		X	X	X
Pregnancy test – females only (urine) c	X		X	X	X
Blood samples for serum concentrations of ADAs					

☐-----☐; AEs=adverse events; ECG=electrocardiogram; FBC=full blood count; SAE=serious adverse event.

# Early Termination could be done by the Sponsor or the Investigator (see Section 3.4, Section 3.5 and Section 9).

a For patients who are not enrolled into the LTE (LTS17367) and require additional safety follow-up.

b A telephone visit is defined as a videoconference, video call or telephone call.

c If urine pregnancy test is positive, a serum control must be done before IMP administration.

d The ICF from the DRI/Phase2b/parent study will not be valid as LTE informed consent. In order for patients to roll over to the LTE a specific LTE ICF will need to be applied, agreed upon and signed at the LTE study, as the LTE is a separated protocol.

**15.4. PCSA Criteria****Table 10 Vital Signs**

Vital Signs	PCSA Criteria
HR	$\leq 50$ bpm and decrease from baseline $\geq 20$ bpm $\geq 120$ bpm and increase from baseline $\geq 20$ bpm
SBP	$\leq 95$ mmHg and decrease from baseline $\geq 20$ mmHg $\geq 160$ mmHg and increase from baseline $\geq 20$ mmHg
DBP	$\leq 45$ mmHg and decrease from baseline $\geq 10$ mmHg $\geq 110$ mmHg and increase from baseline $\geq 10$ mmHg
Weight	$\geq 5\%$ increase from baseline $\geq 5\%$ decrease from baseline

**Table 11 12-Lead ECG**

ECG test	PCSA Criteria
HR	$< 50$ bpm $< 50$ bpm and decrease from baseline $\geq 20$ bpm $< 40$ bpm $< 40$ bpm and decrease from baseline $\geq 20$ bpm $< 30$ bpm $< 30$ bpm and decrease from baseline $\geq 20$ bpm  $> 90$ bpm $> 90$ bpm and increase from baseline $\geq 20$ bpm $> 100$ bpm $> 100$ bpm and increase from baseline $\geq 20$ bpm $> 120$ bpm $> 120$ bpm and increase from baseline $\geq 20$ bpm

PR	>200 ms >200 ms and increase from baseline $\geq 25\%$ > 220 ms >220 ms and increase from baseline $\geq 25\%$ > 240 ms > 240 ms and increase from baseline $\geq 25\%$
QRS	>110 ms >110 msec and increase from baseline $\geq 25\%$ >120 ms >120 ms and increase from baseline $\geq 25\%$
QTCB, QTCF	Absolute values >450 ms >480 ms >500 ms  Increase from baseline Increase from baseline ]30-60] ms Increase from baseline >60 ms
QT	> 500 ms

**Table 12 Clinical Laboratory Parameters**

Laboratory Test	PCSA Criteria
ALT	By distribution analysis: >3 ULN >5 ULN >10 ULN >20 ULN
AST	By distribution analysis: >3 ULN >5 ULN

	>10 ULN >20 ULN
Alkaline Phosphatase	> 1.5 ULN
Total Bilirubin	>1.5 ULN >2 ULN
Conjugated Bilirubin	>35% Total Bilirubin and TBILI>1.5 ULN
ALT and Total Bilirubin	ALT>3 ULN and TBILI>2 ULN
CPK	>3 ULN >10 ULN
Creatinine	≥150 µmol/L (Adults) ≥30% change from baseline ≥100% change from baseline
CLcr (mL/min) (Estimated creatinine clearance based on the Cockcroft-Gault equation)	<15 (end stage renal disease) ≥15 - <30 (severe decrease in GFR) ≥30 - < 60 (moderate decrease in GFR) ≥60 - <90 (mild decrease in GFR) ≥ 90 (normal GFR)
eGFR (mL/min/1.73m  ) (Estimate of GFR based on an MDRD equation)	<15 (end stage renal disease) ≥15 - <30 (severe decrease in GFR) ≥30 - < 60 (moderate decrease in GFR) ≥60 - <90 (mild decrease in GFR) ≥ 90 (normal GFR)
Uric Acid	Hyperuricemia >408 µmol/L Hypouricemia <120 µmol/L
Blood Urea Nitrogen (BUN)	≥17 mmol/L
Chloride	<80 mmol/L >115 mmol/L
Sodium	≤129 mmol/L ≥160 mmol/L
Potassium	<3 mmol/L ≥5.5 mmol/L

Total cholesterol	$\geq 7.74$ mmol/L
Triglycerides	$\geq 4.6$ mmol/L
Lipasemia	$\geq 3$ ULN
Amylasemia	$\geq 3$ ULN
Glucose	Hypoglycaemia $\leq 3.9$ mmol/L and $< LLN$ Hyperglycaemia $\geq 11.1$ mmol/L (unfasted); $\geq 7$ mmol/L (fasted)
HbA1c	$> 8\%$
Albumin	$\leq 25$ g/L
CRP	$> 2$ ULN or $> 10$ mg/L (if ULN not provided)
WBC	$< 3.0$ Giga/L (Non-Black); $< 2.0$ Giga/L (Black) $\geq 16.0$ Giga/L
Lymphocytes	$> 4.0$ Giga/L
Neutrophils	$< 1.5$ Giga/L (Non-Black); $< 1.0$ Giga/L (Black)
Eosinophils	$> 0.5$ Giga/L or $> ULN$ (if $ULN \geq 0.5$ Giga/L)
Monocytes	$> 0.7$ Giga/L
Basophils	$> 0.1$ Giga/L
Hemoglobin	$\leq 115$ g/L (Male); $\leq 95$ g/L (Female) $\geq 185$ g/L (Male); $\geq 165$ g/L (Female) Decrease from Baseline $\geq 20$ g/L
Hematocrit	$\leq 0.37$ v/v (Male) ; $\leq 0.32$ v/v (Female) $\geq 0.55$ v/v (Male) ; $\geq 0.5$ v/v (Female)
RBC	$\geq 6$ Tera/L
Platelets	$< 100$ Giga/L $\geq 700$ Giga/L
pH	$\leq 4.6$ $\geq 8$

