1.6 Summary of Known and Potential Risks and Benefits

Clinical and non-clinical studies confirm that KY1005 exerts the intended pharmacological effect in relevant immune systems, and can provide meaningful clinical improvement in the signs and symptoms of AD. The benefits of KY1005 in moderate-to-severe AD have been demonstrated in the KY1005-CT02 Phase 2a study where both KY1005 treatment groups provided clinically meaningful improvements in the signs and symptoms of disease.

KY1005-specific risks, including none associated with SC administration, have not been identified to date from the non-clinical or clinical programme. Potential risks include malignancy and impaired response to infection (discussed

tested to date. One patient in the prior healthy volunteer study (KY1005-CT01) experienced a reaction of the mouth and throat during systemic administration on first exposure to KY1005. No similar events were noted in the KY1005-CT02 Phase 2a study in AD patients nor the KY1005-CT04 SC healthy volunteer study. Systemic or localised allergic reactions that require immediate treatment are therefore defined as an adverse event of special interest (AESI; see Section 8.1.3) so that specific information can be collected prospectively.

Overall, to date blockade of OX40/OX40L in humans is precedented without acute severe adverse consequences. These findings suggest that OX40L-mediated clearance is not relevant at pharmacological doses and that such binding, in disease states in which OX40L is

upregulated, does not lead to common adverse reactions. Mitigation of the theoretical risks is possible through selection of appropriate study populations and monitoring in clinical trials. The overall benefit risk is therefore in favour of continued development of KY1005 in immune mediated disease such as AD.

Further details can be found in the IB.

1.6.1 Benefit/Risk of KY1005 Regarding Potential Infections with Severe Acute Respiratory Syndrome Coronavirus 2 (SARS-Cov-2)

There is no change in the overall benefit/risk of treating patients with KY1005 regarding the Coronavirus Disease 2019 (COVID-19) pandemic. In case of the implementation of restrictions due to COVID-19, the advice provided in Section 17.14 (Appendix 14) should be followed.

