6.4.4 Standard Laboratory Safety Tests

All standard safety laboratory parameters assessed will be evaluated centrally.

The standard laboratory safety tests consisting of haematology (full blood count [FBC]), clinical chemistry (electrolytes and non-fasting biochemistry) and urinalysis assessments defined in Table 6-5 will be performed throughout the study.

All WOCBP will also have a serum pregnancy test at Screening. Urine pregnancy tests will be performed pre-injection on IMP administration days, and at the early termination visit, Days 393 (Week 56), 449 (Week 64), and 477 (Week 68) of the safety follow-up period. These will be performed locally. If a urine pregnancy test result is positive, it must be confirmed by a serum pregnancy test.

For post-menopausal women only, a blood sample will also be taken at Screening for FSH.

Screening laboratory assessments may be repeated a maximum of once where initial results are in the Investigator's opinion, clinically significant and only provided the initial result is considered a temporary anomaly and there is a documented explanation as to the likely cause of the result (Section 4.6).

All laboratory reports should be reviewed, signed, and dated by a designated physician within 24 hours of receipt. These will be checked and verified by the Study Monitor during monitoring visits.

[figure not shown]
Table 6-5: Standard Laboratory SafetyTests

Category	Parameter
Haematology	WBCC and differentials, RBCC, RDW, Hb, HCT, nucleated red blood cells, platelet count, MCH, MCHC, MCV, and MPV
Clinical chemistry	Albumin, sodium, potassium, chloride, bicarbonate, urea, creatinine, glucose, calcium, phosphate, ALT, AST, GGT, LDH, alkaline phosphatase, total protein, iron, total bilirubin and CPK
Urinalysis	pH, protein, glucose, ketones and blood

ALT=alanine aminotransferase; AST=aspartate aminotransferase; CPK=creatine phosphokinase; GGT=gamma-glutamyl transferase; Hb=haemoglobin; HCT=haematocrit; LDH=lactate dehydrogenase; MCH=mean cell haemoglobin; MCHC=mean cell haemoglobin concentration; MCV=mean cell volume; MPV=mean platelet volume; RBCC=red blood cell count; RDW=red cell distribution width; WBCC=white blood cell count.

Assay methodology and procedures will be described in a laboratory manual to be finalised before the samples are collected. Samples will be shipped to and analysed by PPD Central Laboratory.

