## 9.2 Clinical Laboratory Evaluations

All clinical laboratory summaries will be based on central laboratory data using the conventional units provided by the central laboratory. However, in listings results with both conventional and standard units will be provided.

Descriptive statistics for central laboratory safety parameters including absolute values and change from baseline values will be summarised with n, mean, SD, median, minimum and maximum values by treatment regime and by respective visits and timepoint if applicable.

Analysis of potentially clinically significant abnormality (PCSA) will be performed based on the PCSA criteria. For parameters for which no PCSA criteria are defined, similar analyses will be done using the normal range, if applicable. Analyses according to PCSA will be performed based on the worst value during the treatment emergent period, using all measurements (either local or central, either scheduled, nonscheduled or repeated).

For laboratory variables, vital signs and ECG variables, the incidence of patients with at least one PCSA during the treatment-emergent period including unscheduled, early termination or safety follow-up visits will be summarized regardless of the baseline level and according to the following baseline status categories:

- Normal/missing
- Abnormal according to PCSA criterion or criteria;

Changes in central laboratory data will also be summarized using shift tables from baseline to the worst toxicity grade.

Laboratory data collected at all visits including unscheduled, early termination or safety follow-up visits will be included in listings and will contribute to tables of shifts from baseline and in tables showing change from baseline grade to the worst toxicity grade. Unscheduled laboratory results will not be windowed for the purposes of assigning a nominal visit.

All vital sign, physical examination and ECG data including unscheduled, early termination or safety follow-up visits are mapped to analysis visits and are included in the summary.

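### Lymphocytes have only a high-count abnormality criterion in SAP Table 12, and the normal-range fallback in SAP 9.2 does not reach low counts, so a low lymphocyte count is never counted as a lymphocyte PCSA

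*SAP*

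**What the plan says.** The laboratory screen rests on SAP section 9.2: "Analysis of potentially clinically significant abnormality (PCSA) will be performed based on the PCSA criteria". The criteria are in SAP section 15.4, and those for laboratory tests are in Table 12. The lymphocyte row there reads, in full, "Lymphocytes $> 4.0$ Giga/L".

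SAP 9.2 has a fallback: "For parameters for which no PCSA criteria are defined, similar analyses will be done using the normal range, if applicable". It also says that the PCSA analysis takes the worst value in the treatment-emergent period, from all measurements whether scheduled or not, and reports incidence overall and by baseline status.

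Besides the PCSA tables, SAP 9.2 plans by-visit descriptive statistics with change from baseline, listings, and shift tables: "Changes in central laboratory data will also be summarized using shift tables from baseline to the worst toxicity grade". Protocol section 10.4.2.6 adds a number and percentage of out-of-range values at each timepoint.

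Protocol section 1.6 states the background risk: "Potential risks include malignancy and impaired response to infection". Protocol Table 6-5 lists "WBCC and differentials" among the haematology tests, and Protocol Tables 6-1 to 6-3 schedule the blood count at every dosing visit.

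**The concern.** A PCSA table is the place where a reader looks for individual patients who crossed a limit, compared by arm and using each patient's worst value. For lymphocytes that table works in one direction only. The product blocks a T-cell co-stimulation pathway (Protocol 1.4.1), and infection is a named potential risk, so the low direction is a relevant one to screen.

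The fallback makes the gap easy to miss. A parameter absent from Table 12 would be examined against its normal range. Lymphocytes are less well covered on the low side because they have an entry. If low counts became more frequent with dose, the lymphocyte PCSA row would not show it, and the reader would have to find it in outputs that the SAP specifies less fully.

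**Working it through.** There is no stated figure to reproduce. The check is a reading of Table 12 against the rules in SAP 9.2, with a little arithmetic on whether the white-cell row could stand in.

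**1. Blood-count rows of SAP Table 12 (Giga/L)**

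| Parameter | Low-side criterion | High-side criterion |
|---|---|---|
| Total white cells | < 3.0 (Non-Black), < 2.0 (Black) | ≥ 16.0 |
| Neutrophils | < 1.5 (Non-Black), < 1.0 (Black) | none |
| Lymphocytes | none | > 4.0 |
| Platelets | < 100 | ≥ 700 |

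Haemoglobin and haematocrit also carry both sides. Since neighbouring rows keep both limits and no redaction is marked in the lymphocyte row, a low limit lost in PDF conversion is unlikely.

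**2. Apply the rule.** Does Table 12 define a criterion for lymphocytes? Yes, so the normal-range fallback is not triggered. Does a low value meet the criterion that is defined? Only values above 4.0 do. Hence any value from 0 to 4.0 gives no lymphocyte PCSA.

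**3. Could the white-cell row catch the same patients?** Let W be baseline total white cells and d the loss of lymphocytes, with other cells unchanged. The total becomes W − d, and it is flagged only if W − d < 3.0 (Non-Black) or W − d < 2.0 (Black). That is W < 3.0 + d or W < 2.0 + d. The documents give no baseline counts, so d and W are assumptions shown over a range. With an assumed baseline lymphocyte count of 2.0:

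| Lymphocytes fall to | d | Flagged, Non-Black, only if W is below | Flagged, Black, only if W is below |
|---|---|---|---|
| 1.0 | 1.0 | 4.0 | 3.0 |
| 0.5 | 1.5 | 4.5 | 3.5 |
| 0.4 | 1.6 | 4.6 | 3.6 |
| 0 | 2.0 | 5.0 | 4.0 |

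Example with a fall from 2.0 to 0.4 (d = 1.6): W = 4.0 leaves 2.4, flagged under the Non-Black limit but not under the Black limit. W = 5.0 leaves 3.4, W = 6.0 leaves 4.4 and W = 8.0 leaves 6.4, none of them flagged. The white-cell row therefore catches a lymphocyte fall only in patients whose total was already fairly low, and it counts them as white-cell events. These figures illustrate the rule. They are not a forecast of any fall.

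**4. What else would show a low count?**

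- By-visit statistics (n, mean, SD, median, minimum, maximum): a minimum shows one patient, and a mean dilutes a few deep falls.
- Shift tables to worst grade: these could show it, but SAP 9.2 names no laboratory grading scale and gives no direction for lymphocytes.
- Out-of-range counts: promised in Protocol 10.4.2.6, but not repeated in SAP 9.2, and the protocol does not say that high and low values are split.
- Listings: complete, but with no comparison by arm.

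**The case against.** The strongest reply is that other planned outputs already cover low counts. The SAP is to be read together with the protocol, so the out-of-range counts still stand. The shift tables use central data, but that loses little: Protocol 6.4.4 has all standard safety tests evaluated centrally, and Protocol Appendix 14 keeps emergency local results out of the statistical analyses. Data from unscheduled, early-termination and follow-up visits also feed the shift tables, so they are close to a worst-value analysis of the same data. CTCAE is the only grading scale named in the documents, for adverse events. If it is also meant for laboratory values and grades low lymphocyte counts, the shift table would show them. Severe, opportunistic and persistent infections are tracked directly as events of special interest. Most of this stands, and it limits the consequence. It does not close the gap, because the laboratory scale has to be guessed and the out-of-range counts have dropped out of SAP 9.2.

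Two stronger readings are tempting. A reader might infer that low lymphocyte counts would go unreported. The routes just listed show otherwise, and a row labelled as above 4.0 does not itself claim anything about low counts. A reader might also infer from the mechanism that lymphopenia is an expected effect being overlooked. Protocol 1.4.1 points the other way: it describes an antibody expected to have no effector function and not to deplete the cells it targets. Blocking co-stimulation alters what cells do and need not lower their number.

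**Conclusion.** The gap is real and narrow. Followed as written, the SAP cannot count a low lymphocyte value as a lymphocyte PCSA at any depth, while white cells, neutrophils and platelets have low limits. This conclusion needs no numerical assumption; it follows from one table row and one sentence. The arithmetic on the white-cell row does rest on assumed baseline counts, and it shows only that this row is a partial and indirect substitute.

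The consequence is a one-sided safety screen for a product with impaired response to infection as a named potential risk. Nothing in the documents forecasts lymphopenia, so no expected effect is being missed. A screen is nevertheless there to pick up what is not expected. The point is a cheap improvement and does not threaten the trial's conclusions.

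**What to change.** Make one of two changes before the next database lock.

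- Add a low-side lymphocyte row to SAP Table 12, with a threshold chosen by the sponsor, and report it by arm and by baseline status in the existing PCSA tables.
- Or reword the fallback in SAP 9.2 so that the normal range applies to any direction for which Table 12 gives no criterion.

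The second option reaches further than lymphocytes. It would also bring in directions of less interest, such as a low ALT, unless the existing proviso on applicability is used to exclude them. The first option is the tighter one.

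The cost is one row and one programmed flag, or one sentence, using data already collected. The downside is a few more flagged values to review. The change affects an analysis flag only and alters no dosing, stopping or monitoring rule.
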